### 3.2.16 Pooling of Centres

It is not planned to perform a subgroup analysis on individual or groups of centres. In order to assure that the centre effect will be properly estimated in the statistical models, it is necessary to only consider the centres with a sufficient number of recruited subjects. Therefore, it has been decided to apply the following approach:

- the centres having recruited at least six subjects will be taken into account for the estimate of the centre effect.
- the centres having recruited less than six subjects will be pooled with one (or several) centre(s) within the same country (or across countries within the same region) until the number of subjects in the resulting pooled centre(s) is at least equal to six. Then, only the pooled centre(s) will be taken into account for the estimate of the centre effect.

With such an approach, all the centres (original or pooled) considered for the estimate of the centre effect will account for at least six recruited subjects.

The pooling of small centres will be confirmed at the BDRM prior to unblinding. For the primary efficacy endpoint only, a sensitivity analysis will be conducted in order to investigate homogeneity of treatment response across centres.

### 3.2.17 Interim Analysis

No interim analysis will be performed.

## 3.2.18 Role of Data and Safety Monitoring Board

The DSMB will be composed of independent experts including one independent clinician who specialises in treating paediatric spasticity, one independent statistician and one independent pharmacovigilance expert. Data and Safety Monitoring Board meetings will take place as defined in the charter describing the operation of this committee and will depend on recruitment rate of the study. The first data review will take place after five subjects have been on treatment for at least 6 weeks or 4 months after the first subject has been randomised, whichever occurs first. Subsequent meetings will take place at intervals as defined by this committee.

Safety and efficacy data will be provided to the committee for their review. Possible recommendations that the DSMB can make regarding the conduct of the study are described in the charter. This includes recommending that the study is stopped for safety reasons.

The Chair of the DSMB will be responsible for communicating the committee's recommendations to Ipsen.

## 4 COMPUTER SYSTEMS, SOFTWARE AND VALIDATION OF PROGRAMS

## 4.1 Hardware

The statistical analysis will be performed under the Microsoft Windows operating system.

### 4.2 Software

All statistical analyses will be performed using SAS® Software version 9.4 or later (SAS Institute Inc., Cary, NC, USA).

## 4.3 Validation and QC (Quality Control) Plan

All SAS® programs are checked for logic by the developer and verifier, if applicable. The verification procedures used to ensure SAS® programs work as intended are described in CCI

All programs for the production of analysis datasets and tables, listings, and figures (TLFs) are double programmed by the verifier. Initial programming results and verification programming results are compared electronically. Tables and listings are double programmed and results of the initial programming and the verification programming are compared electronically. The verification process for figures may follow the double-programming process, or by confirming that data points contained in the plot are consistent against a source table or listing.

SAS® Programming" describes the quality control procedures that must be performed for all SAS® programs and outputs. Quality control is defined here as the operational techniques and activities undertaken to verify that the SAS® programs produce the proper clinical study output by checking for their logic, efficiency and commenting and by inspection of the produced output.

Individual output review is performed on all outputs by the statistical reviewer. It includes checking against mocks and checking for overall consistency and accuracy. In addition a Senior Biostatistical Reviewer performs high level review of the outputs to confirm statistical validity and compliance with the associated analysis plan.

A SAS® Programming and Quality Control Plan is prepared to document the methods of validation.

Copies of the QC documentation produced as confirmation that the validation process has been followed will be provided by **CCI** and will be retained by the sponsor.

## 4.4 **Restitution of the Programs**

All programs (including Macros and analysis datasets) producing the tables, listings and statistical output along with associated logs should be given to the sponsor when the tables, listings, figures and statistical analysis has been finalised.

# 5 CHANGES FROM PROTOCOL

- 'Treatment Cycle' is used instead of 'Treatment'
- According to the protocol listings will be sorted by treatment group and subject ID. As the treatment group for a subject can change during the course of the study, listings will be presented by subject ID instead.
- MAS responder analyses in injected muscle group (elbow, wrist and finger flexors) has been added to the tertiary efficacy endpoints.
- GAS responder analyses has been added to the tertiary efficacy endpoints
  - CCI

66/108

- Time to retreatment. The time from injection to retreatment (in weeks) will be summarized by treatment group and overall in the mITT population for subjects retreated at any time from the Week 16 visit onwards. Subjects who are not retreated are censored at the date of their last recorded visit in the treatment cycle or observational phase. Results from the Kaplan-Meier analysis will be obtained using the SAS® LIFETEST procedure. A summary table will present the results from the Kaplan-Meier analysis and will include the numbers of subjects at risk, censored and with an event (retreated) for each time interval, as well as the Kaplan-Meier estimates, the median time to event, and 95% CI. In addition, the Kaplan-Meier estimated survival functions will be plotted. Summary tables for the number and percentages of subjects retreated at each Treatment Cycle from Week 16 onwards and the time to retratment will also be displayed. An individual data listing will present the actual time to retreatment for each subject.
- The sensitivity analysis on the primary and first secondary endpoint to assess the impact of missing values will be performed on the full population of all randomised subjects instead of the population of all randomised subjects who received at least one injection of study treatment.
- According to the study protocol the theoretical maximum dose for the study limb was 640 U in the 16 U/kg group, however, due to the reconstitution of Dysport the maximum actual dose is 650 U.

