4.1.3 Study Structure

At study entry, subjects will be randomised into one of the following three treatment groups for Treatment 1:

- Group A: Dysport 16 U/kg in one upper extremity (the study limb).
- Group B: Dysport 8 U/kg in the study limb.
- Group C: Dysport 2 U/kg in the study limb.

Randomisation will be done with an Interactive Response System (IRS) and will be in a 1:1:1 ratio. The IRS will be used to allocate packs and envelope numbers (to be considered to reconstitute the treatment) and then study treatment reconstitution will be performed by an independent reconstitutor who will not be involved in any other study related activities in order to maintain the blinding.

For Treatments 2, 3 and 4, subjects are planned to receive Dysport 8 U/kg or 16 U/kg according to the treatment allocation by the IRS and will remain double blind throughout the study.

CCI [REDACTED]

The total dose for the study limb must not exceed 320 U in the 8 U/kg group and 640 U in the 16 U/kg group.

The planned retreatment interval is 16 weeks and a maximum of four treatments will be administered.

[figure not shown]
At study entry, a PTMG, either the elbow flexors or wrist flexors, will be nominated by the Investigator. The PTMG can be changed for subsequent treatments, from elbow to wrist flexors or wrist to elbow flexors, provided that the following criteria are fulfilled:

- The Modified Ashworth Scale (MAS) score of the other muscle group not selected for the last treatment (new PTMG) must be higher than the last treatment PTMG, and
- The new PTMG must have a modified MAS score of greater or equal to 1+.

For Treatments 2, 3 and 4, injection into the lower extremity/extremities and the non-study upper limb will be allowed at the same time as the study limb is injected (see Section 9.1.4).

The stages of the study and the planned doses for the study are provided in Figure 1.

Figure 1 Planned Study Structure

Stratification will be performed according to age range (2 to 9 years and 10 to 17 years) and BTX naïve or non-naïve status assessed at baseline.

CCI [REDACTED]

A maximum of four treatments will be administered in this study. After each treatment administration, the follow up visit schedule is as follows:

- Week 2 (telephone call, safety follow up).
- Week 4 (telephone call, safety follow up).
- Week 6.
- Week 12 (telephone call, safety follow up).
- Week 16.

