The study is designed to allow injections into multiple muscle groups in the study limb and since the elbow and the wrist flexors were the most commonly injected upper limb muscles in CCI, the total dose in each treatment group is set to allow concurrent treatment of these two muscle groups. Furthermore, the chosen doses are well within the maximum total dose of 30 U/kg of Dysport (with a maximum total dose of 1000 U) per treatment session for use in lower limb spasticity in children, recommended in the international consensus paper in 2010 [29].

A fixed dosing volume was chosen for the study to eliminate the confounding effect of dilution. The injection volume of 1.6 mL will be sufficient to inject multiple muscles of the upper limb, as required according to clinical need. Proximal and distal muscle groups of the upper limb have different sizes of the muscle bulk and may require different doses and volumes of injection [33]. For Treatments 2, 3 and 4, Investigators will be allowed to adjust the dose, according to treatment response, at the level of individual muscles by changing the injection volume, or total dose by requesting a dose change in the IRS without having to break the blind. Furthermore, for Treatments 2, 3 and 4, injection into the lower extremity/extremities and the non-study upper limb will be allowed at the same time as the study limb is injected. In order to stay within the total body dose of 30 U/kg, maximum 1000 U, CCI

The planned retreatment interval in this study is 16 weeks, as previously conducted paediatric lower limb studies suggest that the effect of Dysport can still be observed 16 weeks after treatment [38,39]. In another study, the treatment interval was 4 months [40].

4.3.1 *Study Population for Analysis*

The primary analysis will be performed on the mITT population (see Section 11.2).

4.3.2 *Study Duration*

The overall duration of the study is anticipated to be approximately 4 years and 9 months and will include subject recruitment (approximately 3 years) and last subject follow up (approximately 1 year and 9 months). The study will be considered to have started when the first subject has provided signed informed consent. The study will be considered to have finished after the last subject has completed the end of study visit.

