Dysport will be reconstituted at the investigational site with preservative free 0.9% sodium chloride for injection. Detailed instructions will be provided for the volume which needs to be withdrawn from the reconstituted Dysport vials according to each subject's body weight and the group. The study treatment will be prepared by an independent reconstitutor (see Section 9.2.2) according to the instruction leaflet allocated for that treatment. The treatment allocation will be kept by the independent reconstitutor and must not be made available to any other members of the study team. A total of 1.6 mL of the reconstituted study treatment will be provided in syringes to the Investigators (or designee) performing the injection. This syringe will be labelled with the subject's study number without any dose information. Thus, the Investigator and subject will be completely blinded to the identity of the study treatment in the syringe and the dose. Regardless of the treatment group to which the subject is allocated, the volume of 1.6 mL will be constant across all dose groups.

All subjects will receive Dysport administered intramuscularly (see Section 9.1.3 for dosage). Electrical stimulation (ES) and/or ultrasound will be used to localise the targeted injection sites. Complementary techniques such as electromyography will be allowed in addition to ES and/or ultrasound. Description of the use of ES will be provided in the Study Manual.

For the injection, each participating centre should maintain their usual injection environment and procedures for their pain management strategies (e.g. use of general anaesthesia, topical anaesthesia, or oral, intranasal or rectal medication). The injection techniques and pain management strategies used will be recorded in the eCRF.

The study limb (left or right), the PTMG, muscles injected and volume injected (total and per muscle) will be documented in the eCRF.

9.1.3 *Treatment of the Study Upper Limb*

9.1.3.1 *Total Dose/Volume in the Study Upper Limb*

Subjects will receive Dysport 2 U/kg, 8 U/kg or 16 U/kg in the study limb in Treatment 1 and are planned to receive Dysport 8 U/kg or 16 U/kg in subsequent treatments according to the treatment allocation by the IRS (Table 1) and both Investigators and subjects will remain blinded to study treatment throughout the study. CCI

[figure not shown]

Table 1 Planned Dysport Dose Administered per Treatment Group

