Group	Number of Subjects	Treatment 1 ^(a)	Treatments 2, 3 and 4 ^(a)
A	70	Dysport 16 U/kg	Dysport 16 U/kg
B	70	Dysport 8 U/kg	Dysport 8 U/kg
C ^(b)	70	Dysport 2 U/kg	Dysport 8 U/kg or Dysport 16 U/kg

^(a) The total dose for the study limb must not exceed 320 U in the 8 U/kg group and 640 U in the 16 U/kg group.

^(b) In this group, dynamic dose dispensing will be done by IRS at Treatment 2 to maintain a balance between subjects receiving 8 U/kg and 16 U/kg.

The dose for each subject will be calculated according to the subject's body weight, up to a maximum body weight of 40 kg (even if the subject weighs more than 40 kg and therefore a maximum total dose of 320 U in the 8 U/kg group and 640 U in the 16 U/kg group, [Table 2](#)). The allocated dose will be reconstituted with preservative free 0.9% sodium chloride for injection to a fixed volume of 1.6 mL for injection.

The IRS will be used to allocate packs and envelope numbers (to be considered to reconstitute the treatment) and then study treatment reconstitution will be performed by an independent reconstitutor who will not be involved in any other study related activities in order to maintain the blinding.

Study treatment will be supplied to the study centre in individual packs. Each pack will contain two vials of 500 U Dysport. The appropriate instruction leaflet, with detailed instructions for reconstitution will be provided outside of the treatment packs: one instruction leaflet for each of the possible doses 2 U/kg, 4 U/kg, 8 U/kg and 16 U/kg. The Sponsor will provide the injection materials (syringes and needles) for paediatric use to sites.

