9.1.3.3 Dose/Volume by Muscle

The entire volume for injection (1.6 mL) will be injected and will be divided between the PTMG (elbow flexors or wrist flexors) and a number of additional muscles selected by the Investigator according to the disease presentation.

The volume injected into the additional muscles must not exceed that specified in the dosing paradigm in [Table 3](#). No more than 0.5 ml will be injected per injection site.

The injection volume, number of injection sites and dose by muscles in the PTMG are provided in Table 2. Those are mandatory for the PTMG at treatment 1 and should be applied at other treatment cycles if clinically indicated.

- If elbow flexors are chosen as the PTMG, both brachialis and brachioradialis have to be injected at the injection volume specified in Table 2.
- If wrist flexors are chosen as the PTMG, both flexor carpi radialis and flexor carpi ulnaris have to be injected at the injection volume specified in Table 2.

Table 2 Injection Volumes, Dose per Muscle and Number of Injection Sites in the Primary Targeted Muscle Group

For Primary Targeted Muscle Group (PTMG)	Injection Volume (mL)	Number of Injection Sites	Dose per Muscle in U/kg / Maximum U		
			Low 2 U/kg	Medium 8 U/kg ^(a)	High 16 U/kg ^(a)
Elbow flexors					
Brachialis	0.6	2	0.75 U/kg/30 U	3 U/kg/120 U	6 U/kg/240 U
Brachioradialis	0.3	1	0.375 U/kg /15 U	1.5 U/kg/60 U	3 U/kg/120 U
Wrist flexors					
Flexor carpi radialis	0.4	1 - 2	0.5 U/kg /20 U	2 U/kg/80 U	4 U/kg/160 U
Flexor carpi ulnaris	0.3	1	0.375 U/kg /15 U	1.5 U/kg/60 U	3 U/kg/120 U

^a The total dose for the study limb must not exceed 320 U in the 8 U/kg group and 640 U in the 16 U/kg group.

CCI

9.1.3.4 Dose/Volume at Treatment 2, 3 and 4

CCI
[Redacted text]

[Redacted text]

[figure not shown]
CCI [Redacted text]

[Redacted text]

[Redacted]	[Redacted]	[Redacted]
[Redacted]	[Redacted]	[Redacted]
[Redacted]	[Redacted]	[Redacted]
[Redacted]	[Redacted]	[Redacted]
[Redacted]	[Redacted]	[Redacted]
[Redacted]	[Redacted]	[Redacted]

[Redacted text]

Figure 2 Dose Modifications Available During the Study

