9.1.3.6 Dosing Interval (Applicable to all Treatments) and reinjection criteria

The planned retreatment interval is 16 weeks and a maximum of four treatments will be administered.

At Week 16, subjects will be assessed for their eligibility to receive the next treatment. Subjects who are eligible for retreatment will be given the next treatment. In the unforeseeable event that the injection cannot be administered at the scheduled visit due to any technical or logistical reasons, an unscheduled visit can be arranged within the 2 week visit window.

The duration of the follow up period will be dependent upon the treatment interval as follows:

- All subjects whose first three treatment intervals fall between ≥ 16 and ≤ 22 weeks will receive four treatments and will exit the study as soon as a new injection is required and no later than 22 weeks after last injection (up to a maximum of 1 year and 9 months study duration).
- All other subjects will not be given any further study treatment after Week 52 and will exit the study after 16 weeks of follow up of the last treatment.

CCI

[Redacted text block]

9.1.4 *Concomitant Treatment of Lower Limb Spasticity and the Non-study Upper Limb*

For Treatments 2, 3 and 4, injection into the lower extremity/extremities and the non-study upper limb will be allowed at the same time as the study limb is injected. Muscle(s) for injection will be selected according to the Investigator’s judgement.

If there is no need to inject the lower limbs, and only the non-study upper limb is to be injected (on top of the study upper limb), the dose in the non-study upper limb should not exceed the dose detailed in Table 5 below:

Table 5 Maximum Dose for Non-study Upper Limb

Body Weight (kg)	Maximum Dose
10 to 40	5 U/kg, calculated up to 40 kg
40 and over	200 U

For dose by muscle, please refer to table 8

If there is no need to inject the non-study upper limb and only one or two lower limb(s) are to be injected (on top of the study upper limb), the dose in the lower limb(s) should not exceed the dose detailed in Table 6 below:

Table 6 Maximum Dose for the Lower Limb(s)

Body Weight (kg)	Maximum Dose
10 to 36	10 U/kg, calculated up to 36 kg
36 and over	360 U

For dose by muscle, please refer to table 9

CCI

[Redacted text block]

CCI

[Large redacted text block]

CCI [Redacted]
[Redacted]
[Redacted]
[Redacted]
[Redacted]
[Redacted]
[Redacted]

No more than 0.5 ml will be injected per injection site.

CCI [Redacted]

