## 8.5 Study Limb Dose in Units

According to body weight and randomised or planned Dysport Dose in U/kg subjects will receive the following Dysport Dose in Units in the study limb (specified in Instuction Leaflet Dysport®, version 7.0 01 March 2017):

| Dyspor              | rt Dose 2 U/kg        |
|---------------------|-----------------------|
| Patient Weight (kg) | Dysport Dose in Units |
| 10                  | 20                    |
| 11                  | 20                    |
| 12                  | 20                    |
| 13                  | 30                    |
| 14                  | 30                    |
| 15                  | 30                    |
| 16                  | 30                    |
| 17                  | 30                    |
| 18                  | 40                    |
| 19                  | 40                    |
| 20                  | 40                    |
| 21                  | 40                    |
| 22                  | 40                    |
| 23                  | 50                    |
| 24                  | 50                    |
| 25                  | 50                    |
| 26                  | 50                    |
| 27                  | 50                    |
| 28                  | 60                    |
| 29                  | 60                    |
| 30                  | 60                    |
| 31                  | 60                    |
| 32                  | 60                    |
| 33                  | 70                    |
| 34                  | 70                    |
| 35                  | 70                    |
| 36                  | 70                    |
| 37                  | 70                    |
| 38                  | 80                    |
| 39                  | 80                    |
| 40                  | 80                    |

| Dyspor              | •t Dose 4 U/kg        |
|---------------------|-----------------------|
| Patient Weight (kg) | Dysport Dose in Units |
| 10                  | 40                    |
| 11                  | 40                    |
| 12                  | 50                    |
| 13                  | 50                    |
| 14                  | 60                    |
| 15                  | 60                    |
| 16                  | 60                    |
| 17                  | 70                    |
| 18                  | 70                    |

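### The dose table in SAP 8.5 gives 650 U at 40 kg, 10 U above the 640 U study-limb limit for 16 U/kg; SAP section 5 discloses this but neither figure is changed

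*SAP*

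**What the plan says.** **The limit.** Protocol 4.1.3 says that the total study-limb dose "must not exceed 320 U in the 8 U/kg group and 640 U in the 16 U/kg group". The same limit appears in Protocol 9.1 and in the footnotes to Protocol Tables 1 and 2. The SAP carries it as current text in section 1.2 and in the footnote to its Table 1.

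**The weight cap.** Under Protocol 9.1.3.1 the dose is calculated by body weight, "up to a maximum body weight of 40 kg (even if the subject weighs more than 40 kg"; the 640 U maximum is presented there as following from this cap.

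**The dose table.** SAP 8.5 states that "subjects will receive the following Dysport Dose in Units in the study limb" and cites instruction leaflet version 7.0 of 1 March 2017. In its 16 U/kg table the 39 kg row is 625 U and the 40 kg row, the last, is 650 U.

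**The per-muscle maxima.** Protocol Table 2 sets volumes, injection sites and maximum units for the muscles of the primary targeted muscle group (PTMG). Section 9.1.3.3 says of these: "Those are mandatory for the PTMG at treatment 1".

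**The disclosure.** SAP section 5 calls 640 U a theoretical maximum and adds that "due to the reconstitution of Dysport the maximum actual dose is 650 U".

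**The concern.** The protocol words the limit as a prohibition, yet a reconstitutor who follows the leaflet exactly will pass it for any child of 40 kg or more on 16 U/kg. No later step would catch this. The whole 1.6 mL is to be injected, and Protocol 9.1.2 says of the labelled syringe: "Thus, the Investigator and subject will be completely blinded to the identity of the study treatment in the syringe and the dose".

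The entry in SAP section 5 tells the reader about the gap without closing it. Protocol 5.1 requires a formal amendment for changes after ethics approval, and a line in the SAP is not one. The SAP itself therefore holds two maxima, 640 U in sections 1.2 and 1.2.1 and 650 U in sections 5 and 8.5. What is at stake is adherence to a stated paediatric dose limit and consistency between documents, not the efficacy inference.

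**Working it through.** **Inputs.** Target dose 16 U/kg; dosing weight capped at 40 kg; limit 640 U (Protocol 4.1.3, 9.1.3.1). The 31 rows of the 16 U/kg table, 10 to 40 kg (SAP 8.5). Injection volume 1.6 mL, with the muscle volumes and maxima of Protocol Table 2.

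**1. The protocol's limit.** 16 × 40 = 640 U. The limit is the nominal dose at the weight cap.

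**2. The leaflet figure.** The step size is not stated; it is inferred from the table. Rounding 16 × weight to the nearest 10 U from 10 to 20 kg, and to the nearest 25 U from 21 to 40 kg, reproduces all 31 rows. At 40 kg: 640 / 25 = 25.6, which rounds to 26, and 26 × 25 = 650 U.

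**3. The excess.** 650 − 640 = 10 U; 10 / 640 = 1.56%; 650 / 40 = 16.25 U/kg.

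**4. Which rows exceed the limit.** Only the 40 kg row is above 640 U; the next highest is 625 U at 39 kg. The 8 U/kg table ends at 320 U, exactly its own limit.

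**5. Per-muscle doses.** Dose per muscle = syringe dose × muscle volume / 1.6 mL.

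| Muscle | Volume (mL) | Table 2 maximum (U) | At 650 U | At 625 U |
|---|---|---|---|---|
| Brachialis | 0.6 | 240 | 243.75 | 234.4 |
| Brachioradialis | 0.3 | 120 | 121.9 | 117.2 |
| Flexor carpi radialis | 0.4 | 160 | 162.5 | 156.25 |
| Flexor carpi ulnaris | 0.3 | 120 | 121.9 | 117.2 |

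The maxima are 640 U divided by volume, so at 650 U each is passed by the same 1.56%. This is the same excess seen by muscle, not a second breach.

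**6. Rounding down instead.** 625 / 40 = 15.625 U/kg; (625 − 640) / 640 = −2.34%. The leaflet already gives 15.625 U/kg at 24 kg (375 U) and at 32 kg (500 U), and less at 21 kg (325 U, 15.48 U/kg).

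**The case against.** The departure is openly recorded in the SAP section meant for departures from the protocol, and a SAP can amend neither the protocol nor a leaflet. The 40 kg row follows the same rounding pattern as the rest of the table. Thirteen of the 31 rows lie above nominal, and four have a larger relative excess: 29 kg (+2.4%), 11 kg (+2.3%), 26 kg (+2.2%) and 23 kg (+1.9%). The documents give no separate safety basis for 640 U beyond 16 × 40. For a child above 40.6 kg (650 / 16), 650 U is less than 16 U/kg of actual weight. The SAP attributes the gap to reconstitution, and the leaflet's reconstitution instructions are not visible, so rounding as the cause is an inference.

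Most of this stands, and it keeps the point small. It does not remove it. The limit is in units and applies whatever the child weighs; no other row crosses it; and disclosure leaves an instruction and a prohibition that cannot both be followed.

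A reader might go further and infer that the total-body maximum is also broken, since Protocol Table 6 allows 360 U in the lower limbs in Treatments 2 to 4 and 650 + 360 = 1010 U. The documents do not support that. Protocol 4.3 begins "In order to stay within the total body dose of 30 U/kg, maximum 1000 U" and is blacked out just where it would say how that maximum is kept. Part of the dosing text in 9.1.4 and the SAP's table for combined limbs are also missing. A further cap may well stand there.

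**Conclusion.** The inconsistency is real and minor. Prepared from leaflet version 7.0, the 16 U/kg dose exceeds the study-limb limit by 10 U (1.6%) for every child of 40 kg or more, and the Table 2 maxima are passed in the same proportion.

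This rests on the 40 kg row being used for all heavier children, which follows from the weight cap, and on the full 1.6 mL being injected. Earlier leaflet versions and the number of children affected are not visible.

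A reader might infer harm or a distorted comparison. Neither is shown. No document gives clinical relevance to 10 U. The efficacy analysis follows the randomised group, so type I error and power are untouched. At 40 kg, 650 U is 16.25 U/kg, which stays in the safety group for more than 12 U/kg (SAP 3.2.1.2).

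**What to change.** Round the 40 kg row of the 16 U/kg leaflet table down to 625 U, the next lower step and the dose already used at 39 kg. This respects the 640 U limit and every Table 2 maximum. The cost is one leaflet row, with the SAP 8.5 copy and the section 5 entry updated to match. The downside is a dose 2.3% under target at 40 kg, somewhat further from nominal than the present 1.6% over, but a shortfall the leaflet already accepts at 24 and 32 kg. No other limit needs to change.

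If dosing is complete, only reporting remains: give the number of subjects who received more than 640 U in the study limb. The subject listing in SAP 3.2.9 shows doses in U/kg, so it does not show a limit in units directly. The summaries in SAP 3.2.9.3 already cover study-limb dose; one count in units would be added there.
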